8.2 BINARY ENDPOINTS

Missing data will not be imputed unless stated otherwise.

8.3 CONTINUOUS ENDPOINTS

Missing data will not be imputed unless stated otherwise.

8.4 PATIENT REPORTED OUTCOMES (PROS)

The questionnaires that will be used in the study (EQ-5D-5L, FACIT-Fatigue and FFbH) are accompanied by rules for replacing missing values. If these rules result in the patient having a missing score at a visit, then the missing values will be assumed to be missing at random.

9 STATISTICAL METHODOLOGY AND STATISTICAL ANALYSES

9.1 STATISTICAL METHODS

Descriptive statistics will be presented to describe patient characteristics. Generally, categorical covariates will be described by frequency distribution while continuous covariates expressed in terms of their mean and standard deviation or median and interquartile range (IQR) as appropriate. Graphical displays may also be used.

9.1.1 ANALYSIS FOR RECURRENT EVENT DATA

In order to account for the possibility that there are multiple events occurring for each patient cox-proportional hazards modeling will be used with adjustment for recurrent events. This involves fitting either the Andersen and Gill or Prentice, Williams and Peterson gap-time models to the data.

For each patient, the data will be split into time periods, then data for each time window should include the patient's status, the time of event (if the event occurred) and the value of each of the factors of interest:

So, for patient A, who had events at M6 and M18, their data could look like this:

Patient	Start	Stop	Treatment Escalation Status	Factor A	Factor B	Factor C
A	0	M6	1	3.9	0.6	-10
A	M6	M12	0	3.0	1.5	-20
A	M12	M8	1	2.8	1.7	-10
A	M18	M24	0	2.2	2.3	-10

The cox proportional hazards model (using PROC PHREG) is then used, including the factors of interest (Section 7.3.1) to determine which, if any of them, have an impact on the rate at which treatment changes occur.

Any potential confounders should be included in the model also (Section 7.3.3).

The estimated event rate will be presented, along with 95% confidence interval and p-value, for each of the covariates of interest. Note: These will not be presented for the variables considered to be confounders.

The number and proportion of people experiencing an event at each time point will be presented.

Supportive tables will also be presented which summarises each of the covariates in the model at each visit.

The analysis will be performed for each type of escalation as defined in section 7.1.1 and overall.

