6. RESEARCH QUESTION AND OBJECTIVES

The objective of this non-interventional study is to identify key factors that are driving treatment decisions by rheumatologists in the treatment of RA patients starting treatment with Tofacitinib in a real world setting. In addition to DAS28 score, the following factors may play an important role: difference between DAS28 at start of therapy and after 3-6 months, physician’s global assessment of disease activity, patient’s global assessment of disease activity, arthritis pain and patient’s satisfaction with drug treatment.

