7.2. Setting

The planned recruitment period is 36 months. With planned observation duration of 24 months per patient, the entire study would thus last for 60 months. The study is to start in October 2017 and will end in October 2022. Overall, about 1500 patients in about 200 centres in Germany are to be included in this non-interventional study.

Figure 1. Timelines

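### The primary recurrent-event Cox model has no stated variance estimator that allows for residual dependence within patients or within the roughly 200 centres

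*SAP*

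**What the plan says.** SAP 9.1.1 is the only place where the primary model is described. It states that "cox-proportional hazards modeling will be used with adjustment for recurrent events" and explains this in the next sentence: "This involves fitting either the Andersen and Gill or Prentice, Williams and Peterson gap-time models to the data". On the data layout it says "For each patient, the data will be split into time periods". PROC PHREG is then run with the six factors of interest and the confounders. For the output it says "The estimated event rate will be presented, along with 95% confidence interval and p-value, for each of the covariates of interest". The analysis is done overall and for each escalation type.

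No other section adds a variance estimator:

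- SAP 9.2.2 and the summary table in 9.2.6 refer back to 9.1.1.
- Protocol 7.9.2.1 names Cox modelling only.
- Centre is not among the confounders in SAP 7.3.3.
- The planned sensitivity analyses change covariates, analysis set and visit assignment, not the variance.
- Protocol 7.12 raises correlation between the factors, but not within patients or centres.

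On the setting, the protocol's aim is to "identify key factors that are driving treatment decisions by rheumatologists" (section 6). Therapy is left to the treating physician (7.1), and "about 1500 patients in about 200 centres in Germany are to be included in this non-interventional study" (7.2).

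**The concern.** The outcome is a clinician's decision. The same clinician also scores one of the six factors, the Physician Global Assessment (Protocol 7.6.11). Some patients and some centres will probably switch more readily than others for reasons that the covariates do not capture. A patient's events are then correlated given the model, and so are the events of patients at one centre. A model-based variance ignores both.

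The study's main conclusion is which factors affect the escalation rate, and it is read from these intervals and p-values. If the intervals are too narrow, a factor that is stable within a patient or shared within a centre is named as a driver too often. The SAP text can be followed to the letter and still give model-based intervals.

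**Working it through.** **Inputs from the documents.** About 1500 patients and 200 centres, so 1500/200 = 7.5 per centre (Protocol 7.2). Eight follow-up visits over 24 months (Protocol 7.5). Baseline hazard of 3.16 events per patient (Protocol 7.7).

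**Event rate implied by the plan's own figures.** Expected events = 3.16 × E[exp(linear predictor)], with the five factors of Protocol 7.7 taken as independent.

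- The two binary factors contribute (0.8 + 0.2 × 0.75)(0.4 + 0.6 × 0.10) = 0.95 × 0.46 = 0.437.
- The three scores contribute 1.444 × 1.374 × 1.463 = 2.903, each term being exp(0.01 × |mean| + 0.5 × 0.01² × SD²).
- Together: 3.16 × 0.437 × 2.903 = 4.01 events per patient. With the sign of the score coefficients reversed: 0.65.
- The stated power of about 50% at 1500 patients for DAS28 ≤ 3.2 corresponds to 1.96²/(0.2 × 0.8 × 0.288²) = 290 events, or 290/1500 = 0.19 per patient. The printed inputs as they stand give nearly 100% power, so the 50% is not reproduced. Correlations among the simulated factors are not given, and this mismatch is a separate matter.

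The plan's figures therefore allow anything from about 0.2 to 4 events per patient.

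**Assumed, not in the documents.** Patient frailty variance θ from 0 to 1.0. Centre frailty variance κ of 0 or 0.25. Share of a factor's variance that is constant within a patient (p) from 0 to 0.5, and shared within a centre (c) of 0 or 0.2. Two-sided 5% test, equal centre sizes.

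**Formula.** For a null time-varying factor, a flat hazard, J = 8 intervals and r events per patient (the Andersen-Gill fit is then a Poisson regression):

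true variance / model-based variance = 1 + r × (A + B), where

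- A = [(1+θ)(1+κ) − 1] × [1 + 7(p+c)]/8 is the within-patient part;
- B = 6.5 × κ × c is the part shared with the 6.5 other patients of the centre.

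A patient-level sandwich captures A but not B; a centre-level sandwich captures both. With θ = κ = 0 the ratio is 1 however many rows a patient has.

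**Worked case** (r = 3.16, θ = 0.5, κ = 0.25, p = 0.4, c = 0.2): A = 0.875 × 0.65 = 0.569 and B = 6.5 × 0.25 × 0.2 = 0.325. The ratio is 1 + 3.16 × 0.894 = 3.82, and √3.82 = 1.96. Rejection = 2[1 − Φ(1.96/1.96)], about 32%. After a patient-level sandwich, the remaining SE ratio is √(3.82/2.80) = 1.17, giving about 9%.

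**Simulation** (600 runs per row, 1500 patients, 200 centres; Monte Carlo SE about 0.9 points at 5% and 1.8 points at 25%). Rejection of a true null:

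| r | θ | κ | p | c | SE ratio | Model-based | Patient sandwich | Centre sandwich |
|---|---|---|---|---|---|---|---|---|
| 3.16 | 0 | 0 | 0.5 | 0 | 1.02 | 5.7% | 5.7% | 5.8% |
| 3.16 | 0.5 | 0 | 0 | 0 | 1.09 | 7.3% | 5.3% | 5.8% |
| 3.16 | 0.5 | 0 | 0.5 | 0 | 1.36 | 16.3% | 5.0% | 5.7% |
| 3.16 | 1.0 | 0 | 0.5 | 0 | 1.75 | 26.3% | 7.3% | 7.8% |
| 3.16 | 0.5 | 0.25 | 0.4 | 0.2 | 2.04 | 33.7% | 10.2% | 6.5% |
| 3.16 | 0 | 0.25 | 0.4 | 0.2 | 1.62 | 21.5% | 12.8% | 4.8% |
| 1.0 | 0.5 | 0.25 | 0.4 | 0.2 | 1.31 | 14.5% | 6.0% | 4.0% |
| 0.19 | 0.5 | 0.25 | 0.4 | 0.2 | 1.05 | 6.0% | 4.8% | 4.7% |

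The formula gives 5%, 7%, 15%, 24%, 32% and 22% for the six model-based entries at r = 3.16, in line with the simulation.

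A separate simulation used milder centre effects (κ 0 to 0.2, c 0 to 0.1, θ 0.5 to 1.0, 400 runs per setting). It gave model-based rejection of 5% to 14% at 1.5 to 3.16 events per patient and 3% to 9% at 0.65. With the centre-level sandwich, rejection was 2% to 7% throughout.

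**The case against.** **The SAP is silent; it does not prescribe model-based intervals.** A reader might infer that it does. The text says only that recurrent events are adjusted for, and the authors may have had a robust variance in mind. This stands as to intent. But the phrase is explained solely by a choice between two model families. An analyst who adds the customary patient-level sandwich would still leave centre clustering uncorrected (10.2% and 12.8% in the two centre settings at 3.16 events per patient).

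**Repeated rows are not the problem.** A reader might infer that splitting patients into start-stop rows invalidates the variance. It does not: without frailty the test holds its level under all three variances.

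**The magnitudes are assumed.** Frailty is what remains after 16 confounder terms, and it could be small. The simulations differ according to the values chosen. This stands, and no single inflation figure should be carried forward.

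**The stakes are partly descriptive.** SAP section 5 states no hypothesis, significance level or decision rule and speaks of a predictive model. The 5% test is an assumption made here. Intervals and p-values are nevertheless promised for each factor, and intervals that are too narrow also misstate precision.

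**Choice of model.** A reader might infer that Andersen-Gill must be primary because the sample-size simulation used a total time scale. That does not follow. Patients are followed after leaving tofacitinib, so the hazard may change with event number, which the gap-time model handles by stratifying. Either choice is defensible; leaving it open is not.

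**Conclusion.** The omission is real at both the patient and the centre level, and the SAP should be amended. Whether the intervals will in fact be too narrow cannot be determined from the documents.

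The excess grows with the product of event rate, residual frailty variance and persistence of the factor. Under the assumed values it runs from none (no frailty) or little (about 0.2 events per patient) to roughly 14% to 34% rejection for persistent time-varying factors at about 3 events per patient. A factor with no persistence stays near 7% even at that rate.

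Simulations with factors fixed over time give larger figures, 24% to 49% at frailty variances of 0.25 to 1.0 and about 3 to 4 events per patient. A reader might take these as the expected error. They do not fit the SAP, which lets the factor values change from row to row. Unequal centre sizes, and the separate models for each escalation type, were not examined.

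**What to change.** In SAP 9.1.1, before database lock:

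1. State that the confidence intervals and p-values of the primary model use the robust sandwich variance aggregated by centre. Patients are nested in centres, so this also covers repeated events within a patient.
2. Add the patient-aggregated sandwich as a sensitivity analysis, particularly for escalation types with few events, where a centre-level estimate may be unstable.
3. Name either the Andersen-Gill or the gap-time model as primary and report the other as sensitivity analysis. SAP 4.1 says that no modelling was done at the interim analyses, so the choice can still be made without sight of model results.

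The cost is a few sentences and an option in the procedure already planned. Intervals will be somewhat wider if dependence is present. If it is absent, little is lost: the simulated level without frailty is the same under all three variances.

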6.1. Endpoints

6.1.1. Primary Endpoint:

Impact of the following factors on the number of treatment escalations of Tofacitinib patients in 24 months

- a. DAS28-4 with Erythrocyte Sedimentation Rate (ESR)
- b. Δ DAS28-4 (ESR)
- c. Physician Global Assessment of Arthritis
- d. Patient's Assessment of Arthritis Pain
- e. Patient's satisfaction with drug treatment
- f. Patient's Global Assessment of Arthritis

Treatment escalation in this study is defined as a switch to another DMARD or combination of DMARDs when compared to the last visit.

6.1.2. Secondary Endpoints:

- a) Time to first treatment escalation
- b) Rate of Low Disease Activity (LDA) over time of patients on Tofacitinib (in combination therapy or monotherapy), as assessed by: Simplified Disease Activity Index (SDAI) \leq 11; Clinical Disease Activity Index (CDAI) \leq 10; DAS 28-4 (ESR) \leq 3.2 and DAS28-4 with C-reactive Protein (CRP) \leq 3.2.
- c) Rate of remission over time of patients on Tofacitinib (in combination therapy or monotherapy), as assessed by: American College of Rheumatology (ACR)-EULAR Boolean remission criteria; SDAI \leq 3.3; CDAI \leq 2.8; DAS 28-4 (ESR) $<$ 2.6 and DAS28-4 (CRP) $<$ 2.6
- d) Change from baseline over time of patients on Tofacitinib (in combination therapy or monotherapy) in DAS 28-4 (ESR) and DAS 28-4 (CRP)
- e) Change from baseline of duration of morning stiffness over time of patients on Tofacitinib (in combination therapy or monotherapy)

- f) Change from baseline in the Functional Ability Questionnaire Hannover (FFbH) over time of patients on Tofacitinib (in combination therapy or monotherapy)
- g) Rate of patients with functional remission in FFbH (FFbH > 83%) over time of patients on Tofacitinib (in combination therapy or monotherapy)
- h) Change from baseline in a self-report questionnaire (a quality of life instrument) developed by the European Quality of Life (EuroQoL) Group (EuroQoL EQ-5D) over time of patients on Tofacitinib (in combination therapy or monotherapy)
- i) Change from baseline in Functional Assessment of Chronic Illness Therapy (FACIT)-Fatigue scale over time of patients on Tofacitinib (in combination therapy or monotherapy)
- j) Drug survival at month 12, 24 of patients on Tofacitinib (in combination therapy or monotherapy)
- k) Patient's satisfaction with Tofacitinib treatment (in combination therapy or monotherapy) over time

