7.6.5. Treatment of Rheumatoid Arthritis (RA-Treatment) with Tofacitinib and/or other DMARDs

At each visit (visits 1-9) dose and route of administration (if applicable) of treatment with Tofacitinib and/or other DMARDs will be documented. If an escalation (as defined in section 6.1.1) occurred since the last visit, in addition stop date of previous DMARD(s), start date of new DMARD(s) and reason for switch (lack of efficacy or intolerance) will be documented.

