7.6.19. Safety

All adverse events (AEs) that will occur during the observation period will be documented. At the final visit or if a patient is switched from Tofacitinib to another DMARD, the HCP will be asked to assess the general tolerability of the treatment with Tofacitinib and the reasons for discontinuation (intolerability or lack of efficacy) will be analysed.. Patient's satisfaction with drug treatment will be assessed as described in section 7.6.16.

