7 ENDPOINTS AND COVARIATES

7.1 EFFICACY/ EFFECTIVENESS ENDPOINT(S)

7.1.1 PRIMARY ENDPOINTS

Number and timing of treatment escalations of tofacitinib patients in 24 months, where Treatment Escalation in this study is defined as a switch to another DMARD or combination of DMARDs when compared to the last visit.

The following types of escalations will be distinguished:

1. Treatment **Termination**, which is the termination of a DMARD (or multiple when on combination therapy) without starting a new DMARD therapy. Premature study terminations (without documented treatment termination) will not be considered treatment terminations.
2. Treatment **Step-up** which is an increase from the current treatment regime towards e.g. a combination of DMARDs
3. Treatment **Step-down**, which is a de-escalation from the current treatment regime, e.g. from combination therapy to monotherapy

Patients start their therapy at baseline with tofacitinib either in Monotherapy or in Combination therapy with MTX. Subsequent therapy changes are documented on eCRF instrument “Rheumatologische Medikation“ by:

- adding additional DMARDs on top of the current therapy
- stopping the current DMARD in monotherapy and adding a new DMARD
- stopping one of multiple DMARDs when on combination therapy
- stopping one of multiple DMARDs when on combination therapy and adding a new DMARD
- stopping all DMARDs and not starting a new therapy. The escalation types depend on the combination of DMARD classes (tsDMARD vs bDMARD vs TNFi vs csDMARD). The eCRF does not explicitly distinguish between tsDMARD vs bDMARD vs TNFi, but combines all rheumatic medications belonging to the above classes under

tsDMARD/bDMARD. For the definition of treatment escalations, the following assignment of rheumatic medication to DMARD classes will be done:

tsDMARDs:

- baricitinib
- upadacitinib
- filgotinib

TNFi:

- etanercept
- adalimumab
- certolizumab
- golimumab
- infliximab

bDMARDs (excluding TNFi):

- abatacept
- rituximab
- anakinra
- tocilizumab
- sarilumab

For details of treatment escalations, e.g., which DMARD class addition or reduction leads to a particular escalation type, see table 12.2 in section 12.1.2.

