7.3.3 POTENTIAL CONFOUNDERS TO BE INCLUDED IN THE PRIMARY ANALYSIS

A number of potential confounders will also be included in the primary analysis and all sensitivity analyses:

- Age at baseline
- Gender
- Duration of disease at baseline
- Indicator of tofacitinib dose
 - 1 if recommended dose of 5mg per day (i.e. TofInterval = BID),
 - 0 if reduced dose of 2.5mg per day (i.e. TofInterval = Daily).
- Poor prognostic factors (PF) indicator (1 if at least one Poor PF is present, 0 otherwise)
- Indicator of dose of MTX or combination partner (1 if increase in dose since last visit, 0 otherwise)
- Indicator of dose of Glucocorticoids (1 if increase in dose since last visit, 0 otherwise)
- Whether patient on 2nd or 3rd line treatment (see below)

A patient is defined as on 2nd line treatment if they were prescribed only csDMARDs prior to enrolling in the study.

A patient is defined as on 3rd line treatment if they were prescribed bDMARDs prior to enrolling in the study.

For a list of the medications considered to be csDMARDs and bDMARDs please see the eCRF.

- Indicator of tolerability issues (1 if treatment termination due to tolerability issues, 0 otherwise).
- Indicator of efficacy issues (1 if treatment termination due to efficacy issues, 0 otherwise).
- Incidence of the following comorbidities documented at the baseline visit (a term will be fitted for each comorbidity with the value 1 if the comorbidity is recorded for a patient or 0 otherwise):
 - Ischemic cardiovascular disease
 - Malignancies
 - Infections
 - Gastro disease
 - Osteoporosis
 - Depression

Any other variables observed to be potential confounders will also be investigated.

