12.1.2 DEFINITION OF TREATMENT ESCALATIONS

Table 11.2 provides an overview of all possible treatment switch combinations relevant for the analysis of the primary endpoint and defines the type of escalations, e.g., whether the treatment switch relates to a step-up, step-down or termination.

Table 12.2: Definition of treatment escalations

Therapy*	Mono Tofa	Mono tsDMARD	Mono csDMARD	MonoTNFi	Mono bDMARD	Combo+ csDMARD	Combo tsDMARD +csDMARD	ComboTNFi +csDMARD	Combo bDMARD+ csDMARD	Therapy Stop
MonoTofa	-	Step-up		Step-down	Step-up	Step-up	Step-up	Step-up	Step-up	Treatment termination
Mono tsDMARD	Step-up	Step-up if different tsDMARD		Step-down	Step-up	Step-up	Step-up	Step-up	Step-up	Treatment termination
Mono csDMARD	Step-up	Step-up	Step-up if different csDMARD		Step-up	Step-up	Step-up	Step-up	Step-up	Treatment termination
MonoTNFi	Step-up	Step-up		Step-down	Step-up if different TNFi	Step-up	Step-up	Step-up	Step-up	Treatment termination
Mono bDMARD	Step-up	Step-up		Step-down	Step-up	Step-up if different bDMARD	Step-up	Step-up	Step-up	Treatment termination
Combo+ csDMARD	Step- down	Step-up		Step-down	Step-up	Step-up	Step-up if different csDMARD	Step-up	Step-up	Treatment termination
Combo tsDMARD +csDMARD	Step-up	Step-up if different tsDMARD; Step-down otherwise		Step-down	Step-up	Step-up	Step-up if different tsDMARD or csDMARD	Step-up	Step-up	Treatment termination
Combo TNFi + csDMARD	Step-up	Step-up		Step-down	Step-down, if same TNFi, Step-up if different TNFi	Step-up	Step-up	Step-up if different csDMARD/TN Fi	Step-up if different bDMARD or csDMARD	Treatment termination
Combo bDMARD+ csDMARD	Step up	Step up		Step down	Step up	Step down if same bDMARD; Step-up otherwise	Step up	Step up	Step up	Step up if different bDMARD or csDMARD
*) Definitions:			Mono tsDMARD= Monotherapy any tsDMARD other than Tofa Mono csDMARD= Monotherapy any csDMARD Mono TNFi= Monotherapy any TNFi Mono bDMARD= Monotherapy any bDMARD other than TNFi Combo Tofa= Combination therapy tofacitinib with any csDMARD Combo csDMARD= Combination therapy tofacitinib + any csDMARD				Combo tsDMARD + csDMARD= Combination therapy tsDMARD other than tofacitinib + any csDMARD Combo TNFi + csDMARD= Combination therapy any TNFi+ any csDMARD Combo bDMARD + csDMARD= Combination therapy bDMARD other than TNFi+ anycsDMARD			

PPD

PPD

PPD

LEGAL DISCLOSURE

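### The primary models count switches for intolerance and for lack of efficacy as one event, and no model by recorded reason is planned

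*SAP*

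**What the plan says.** **Event.** Protocol 6.1.1: "Treatment escalation in this study is defined as a switch to another DMARD or combination of DMARDs when compared to the last visit". SAP 7.1.1 repeats this. The reason for the switch is not part of the definition.

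**Split.** SAP 12.1.2 classifies each change by "whether the treatment switch relates to a step-up, step-down or termination", and SAP 9.1.1 follows that classification: "The analysis will be performed for each type of escalation as defined in section 7.1.1 and overall". The sensitivity analyses in SAP 9.2.2 and the 9.2.6 table vary the covariates, the analysis set and the visit to which a switch is assigned. None is run by reason.

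**Reason.** Protocol 7.6.5 has it collected at each escalation: "start date of new DMARD(s) and reason for switch (lack of efficacy or intolerance) will be documented". In the safety section, Protocol 7.6.19 adds for tofacitinib that "the reasons for discontinuation (intolerability or lack of efficacy) will be analysed". The SAP's drug-survival sections (7.1.2.10, 9.2.3.10) do not use it.

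**Covariates.** SAP 7.3.3 lists two reason-based terms among the confounders for the primary and all sensitivity analyses: "Indicator of tolerability issues (1 if treatment termination due to tolerability issues, 0 otherwise" and "Indicator of efficacy issues (1 if treatment termination due to efficacy issues, 0 otherwise".

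**The concern.** The study asks which of six factors (DAS28, its change, physician global, patient global, pain and satisfaction) drive treatment decisions. A switch for uncontrolled disease and a switch after an adverse reaction are different decisions, and the same factor can relate to them differently.

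A pooled ratio cannot show which is at work. The rationale (Protocol section 5) is that criteria other than DAS28 may guide decisions. A weak DAS28 ratio could mean that physicians give DAS28 little weight, or that many switches were for intolerance in patients whose disease was controlled. A strong satisfaction ratio could mean that satisfaction tempers escalation for active disease, or that patients who tolerate a drug badly are dissatisfied with it and come off it. These readings have different implications, and the recorded reason would help to separate them.

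**Working it through.** **1. Does the step-up model separate the reasons?** In Table 12.2 (SAP 12.1.2), a move from tofacitinib monotherapy to another tsDMARD is a step-up. With the columns aligned so that the entry about a different TNFi falls where the TNFi row meets the TNFi column, a move from tofacitinib to a TNFi is also a step-up. A patient in low disease activity (LDA) who makes that move for intolerance is therefore the same step-up event as a patient who makes it for uncontrolled disease. Direction does not stand in for reason.

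**2. Effect of pooling on a hazard ratio.** Let q be the share of switches at the factor's reference level that are for intolerance, HR_E the ratio for efficacy switches and HR_I the ratio for intolerance switches. The two hazards add, so

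pooled HR = (1 − q) × HR_E + q × HR_I.

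This describes a model without the 7.3.3 indicators (step 4). The documents do not give q; 10 to 50% is assumed.

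*Factor unrelated to intolerance (HR_I = 1), HR_E = 0.75.* At q = 20%: 0.8 × 0.75 + 0.2 = 0.80. At q = 50%: 0.5 × 0.75 + 0.5 = 0.875.

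*Factor related to intolerance.* Take an assumed satisfaction HR_E of 0.80 per point and q = 30%:
- HR_I = 1.0: 0.7 × 0.80 + 0.3 × 1.0 = 0.86
- HR_I = 0.8: 0.56 + 0.24 = 0.80, unchanged
- HR_I = 0.6: 0.56 + 0.18 = 0.74, further from 1

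**3. Does splitting cost too many events?** Protocol 7.7 states about 50% power for LDA at 1500 patients, with coefficient −0.288 (HR = exp(−0.288) = 0.75) and 20% of patients in LDA. I could not reproduce that from the stated 3.16 events per patient: 1500 × 3.16 = 4740 events gives √(4740 × 0.2 × 0.8) × 0.288 − 1.96 = 5.97, or power above 99.9%. The correlation between factors and the simulation settings are not given, so I record this as not reproduced, and it is a separate matter. Working back, 50% power needs 1.96² / (0.16 × 0.288²) ≈ 289 events. I use 289 only as a calibration, with two-sided 0.05 assumed from the planned 95% intervals.

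Pooled power = Φ(√(289 × 0.16) × |ln pooled HR| − 1.96). Efficacy-specific power = Φ(√(289 × (1 − q) × 0.16) × 0.288 − 1.96), which approximates the efficacy share of all events by 1 − q. With HR_I = 1:

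| q | 10% | 20% | 30% | 40% | 50% |
|---|---|---|---|---|---|
| Pooled HR | 0.775 | 0.80 | 0.825 | 0.85 | 0.875 |
| Pooled power | 41% | 33% | 26% | 20% | 15% |
| Efficacy-specific power (HR 0.75) | 46% | 42% | 37% | 33% | 28% |

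If LDA is unrelated to intolerance switches, the efficacy-specific model has more power at every q, despite fewer events. If HR_I equals HR_E, the pooled model keeps its power and the split model loses some.

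**4. Do the 7.3.3 indicators separate the reasons?** The SAP does not say whether a treatment termination here means only the Termination type of 7.1.1 (stopping with no new DMARD) or any stopped drug, as 7.1.2.10 uses the word for tofacitinib. Nor does it say to which interval the value attaches. A visit-level simulation (1500 patients, 8 visits, assumed HR_E = 0.50, q = 30%, value attached to the interval that ends in the event) gave:

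| Model | HR for the factor |
|---|---|
| Pooled, no indicator | 0.65 |
| Efficacy-specific | 0.49 |
| Tolerability indicator only | 0.49 |
| Both indicators, Termination type only (assumed 30% of events) | 0.63 |
| Both indicators, every switch | not estimable (SE about 1700) |

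The SAP specifies both indicators, so the last two rows apply. On the narrow reading, a switch to a new drug scores 0 on both and most of the dilution remains. On the broad reading, the indicators predict the event perfectly.

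**The case against.** **The objective is not limited to efficacy decisions.** Protocol section 6 asks about treatment decisions in a real-world setting. An all-reason event is a legitimate target, and this stands. A reader might infer that the all-reason model is wrong, or that an efficacy-only model should replace it. The documents do not support that. It would be a different estimand, and Protocol 7.9 sends major changes to the primary endpoint or its analysis to a protocol amendment.

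**Shrinkage is not general.** A reader might infer that all six ratios are biased toward 1. They need not be. The satisfaction question (Protocol 7.6.16) concerns the drugs received, so intolerance can plausibly drive the answer; patient global and pain may be affected too. Step 2 shows that the pooled ratio can then stay put or move away from 1.

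**The planning ratios are already all-reason.** It is tempting to dilute the protocol's 0.75 and 0.10 and call the result the loss. Protocol 7.7 assumes those values for treatment escalation, which means any switch, so they are not efficacy-specific. The 0.75 above is only a convenient example.

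**Reason is not ignored.** It enters through 7.3.3 and the discontinuation summary in Protocol 7.6.19, and Protocol 7.12 allows further sensitivity analyses. None of these is a pre-specified model by reason, and step 4 shows why the covariates cannot replace one.

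**Conclusion.** The point holds as a missing analysis. Reason is recorded at each escalation, the direction split does not separate reasons, and the two indicators do not repair this under either reading of termination.

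Its size cannot be fixed from the documents. The move from 0.75 to 0.80–0.875 rests on an assumed 20 to 50% intolerance share at the reference level, a factor unrelated to intolerance, and a model without the 7.3.3 terms. The indicator results rest on the further assumptions in step 4.

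A reader might also infer that a weak DAS28 effect in the final report would be purely a product of event mix. That goes too far: Protocol 7.12 itself raises correlated factors as another explanation. What can be said is that the planned models could not tell these explanations apart. This is a cheap improvement, not a flaw that invalidates the primary analysis.

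**What to change.** In SAP 9.1.1 and 9.2.2, keep the all-reason model as the overall primary analysis. Add pre-specified cause-specific recurrent-event models by recorded reason: lack of efficacy, intolerance, and no reason recorded. In each, a switch for another reason ends the current at-risk interval without counting as an event, and the patient re-enters on the new regimen.

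Remove the tolerability and efficacy indicators from SAP 7.3.3 and the 9.2.6 table. Protocol Table 6 names tolerability as a potential confounder but leaves its definition to the SAP; the split by reason can take over that role without a covariate derived from the event.

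The cost is an SAP amendment and extra model runs on data already collected. The primary endpoint is unchanged, and the two indicators appear only in the SAP. The drawbacks are fewer events in each reason-specific model and reliance on the physician's stated reason. If the database is already locked, report the added models as post hoc.
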